7.2. Prohibited concomitant therapies

The following treatments are prohibited during the study treatment period, and the subject must be asked whether he/she has received any new drug at each visit.

- Systemic chemotherapy or biologic therapy other than the study drug that has antineoplastic effects (except for cytokines used to treat adverse events caused by chemotherapy) and Chinese patent medicine with antineoplastic effects.
- Drugs with immunoregulatory effects, including but not limited to non-specific immunoregulators (e.g., thymosin, interferon, interleukin, immunoglobulin, gamma globulin), and Chinese patent medicines with immunoregulatory effects.
- Chemotherapeutic agents that are not stipulated in this protocol.
- Investigational drugs other than sintilimab.
- Radiotherapy used to control tumors (palliative radiotherapy is permitted as long as it is not used for the target lesion, such as radiotherapy for alleviating pain from bone metastases and symptoms of brain metastases).
- Live vaccines during the study. Injections of inactivated influenza vaccine for seasonal influenza are permitted, but live attenuated influenza vaccines for intranasal use are prohibited.
- Corticosteroids. Inhalational steroids are permitted for patients with asthma or chronic obstructive pulmonary disease. Corticosteroids are permitted for temporary use to alleviate dyspnea. Corticosteroids are permitted for the treatment of immune-related AEs. Note: Prophylactic use of corticosteroids to prevent anaphylaxis (e.g., pretreatment before intravenous administration of contrast agent or chemotherapy drug) is permitted.
- Prohibited drugs mentioned in the exclusion criteria.

8. Schedule of Events

This trial comprises three stages (screening period, treatment period, and end of treatment) after each patient signs the informed consent form.

8.1. In the screening period (Day-28 to Day-1), the following study procedures must be completed to ensure that the subject is eligible for this study:

- The informed consent form has been signed;

- Review of inclusion and exclusion criteria;
- Medical history including but not limited to demographic data, past medical history, past treatment history for endometrial cancer, and past and concomitant medications.
- Physical examination: height, weight, body surface area, vital signs (heart rate, blood pressure), comorbidities, and other discomforts;
- ECOG scoring;
- Electrocardiography (within 3 days before the 1st dose)
- Blood routine/blood biochemistry/urine routine/stool routine (within 3 days before the 1st dose);
- Coagulation function tests (within 3 days before the 1st dose);
- Pregnancy test;
- Thyroid function test;
- HIV antibodies, Hepatitis B-five test (HBsAg, HBsAb, HBcAb, HBeAg, HBeAb) and HBV-DNA (if the subject is positive for HBsAg and HBeAg), HCV antibody and HCV-RNA (if the subject is positive for HCV antibody);
- Evaluation of adverse events;
- Radiologic tumor evaluation;
- Pathology consultation
- Archived or fresh tumor tissue samples (non-essential).

8.2 Test items during the treatment period

- Physical examination: weight, vital signs, ECOG scoring once before each dose;
- 12-lead electrocardiography;
- Blood routine (3 days before dosing in every treatment course and once a week during treatment, the number of tests can be increased if $WBC < 3.0 \times 10^9/L$, $N < 1.5 \times 10^9/L$, $Hb < 80g/L$, $PLT < 75 \times 10^9$).
- Blood biochemistry (3 days before dosing in every treatment course);
- Stool and urine test (3 days before dosing in every treatment course);
- Coagulation function test (3 days before dosing in every treatment course);

- Tumor markers (should at least include CA125, CA199, and HE4): tested once before dosing in every treatment course until tumor progression or when the investigator deems it necessary to increase the number of tests;
- Thyroid function test once before dosing in the 1st and 2nd treatment courses and once every 3 treatment courses thereafter;
- HBV-DNA and/or HCV-RNA (if applicable, once every 2 cycles);
- Adverse event evaluation (closely monitored items during drug administration include blood pressure abnormalities, hand-foot-skin reaction, nausea, vomiting, diarrhea, fever, and fatigue). Grading is performed according to CTCAE v4.03.
- Recording of concomitant medications;
- Radiologic tumor evaluation (see Table 1 for details)
 - Administration of investigational drug;
 - Quality of life evaluation.

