Hepatitis B, hepatitis C test ¹⁰	X				If positive, hepatitis B DNA and hepatitis C RNA will be measured on d1 ± 7d in every 2 cycles					
HIV test ¹⁰	X									
Pregnancy test ¹¹	X									

12-lead electrocardiogram		X			X			X	X	
Clinical evaluation examination										
ECOG scoring	X				X					
Evaluation of adverse events ¹²	From the signing of the informed consent form to 30 days after the last dose									
Quality of life questionnaire ¹³		X			X ⁸				X	
Administration of investigational product										
IBI308 administration		X			X					
Anlotinib administration	Administration is recorded daily on d1–d14 of every treatment cycle									
Efficacy evaluation										
Radiologic tumor evaluation ¹⁴	X	Evaluation is performed once after the 2nd treatment cycle (C3) and once after the 4th treatment cycle (C5). Subsequently, an evaluation will be performed once after the 7th cycle (C8) and once after the 10th cycle (C11). After the 10th cycle, an evaluation will be performed once every 4 treatment cycles, and the time window for radiological evaluation is ± 7 days.								
Follow-up after treatment has ended										

Progressive disease	Radiologic evaluation is performed every 3 months after the last dose until disease progression						
Biomarker exploration							
Biomarker blood sampling/sample collection	X						

1. The informed consent form should be signed by subjects before any procedures outlined in the protocol.
2. Vital signs include body temperature, pulse, respiratory rate, and blood pressure.
3. Height is only measured during the screening period. Weight is measured before every dose, except for physical examination during the screening period; physical examination abnormalities during the trial only need to be recorded in the CRF.
4. Routine blood tests include RBC, HGB, HCT, WBC, PLT, and white blood cell categories [LYM, ANC, MONO, EOS, BASO].
5. Blood chemistry includes liver function tests [TBIL, ALT, AST, γ -GT, ALP, ALB, TP, LDH], renal function tests [UREA, Cr], blood electrolytes [Na, K, Cl, Mg], amylase, lipase, blood lipids [total cholesterol (CHO), triglycerides (TG), high-density lipoprotein cholesterol, low-density lipoprotein cholesterol], and fasting blood glucose.
6. Routine urine tests include UWBC, UPRO, URBC, UGLU. Any subjects with $\geq 2+$ proteinuria in routine urine tests must undergo 24-hour urine protein quantification during the screening period.
7. Routine stool test should include stool routine.

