5.2 Treatment protocol

- IBI308 (sintilimab) 200 mg/d, d1, intravenous chemotherapy, q3w.

In this study, the administration method for sintilimab is mainly based on safety and exposure (concentration)-response (PD-1 receptor occupancy) relationship data in earlier studies. Under the premise that no significant abnormality in drug clearance is observed in the subject, it is expected that a steady state can be achieved by continuous infusion of BI308 sintilimab 200 mg q3w for 84 consecutive days (4 times). The expected mean trough concentration at steady state is approximately 26 $\mu\text{g/mL}$, and peripheral and target organ PD-1 receptor occupancy can be maintained. The maximum treatment duration of sintilimab is 24 months. During the study, subjects will receive continuous treatment until a protocol-stipulated treatment termination event occurs.

- Anlotinib hydrochloride: 12 mg/tablet, qd, po, d1-d14, q3w.

Until disease progression or an intolerable adverse reaction occurs. If a missed dose occurs, an additional dose should not be taken if the next dose is less than 12 hours. If the investigator determines that continuing oral anlotinib can benefit the patient at the end of the study, oral anlotinib can continue after the patient has signed the informed consent.

6. Dose Modification

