6.4 Dose modification for anlotinib

If the investigator confirms that toxicity is mainly caused by anlotinib, dose reduction for

anlotinib alone is acceptable. If toxicity caused by 2 or more drugs cannot be confirmed, dose reduction should be performed for all related drugs. If anlotinib dosing is delayed during treatment (3 weeks per cycle), all future dosing dates will be delayed to ensure that the dosing interval between anlotinib treatment cycles is 21 ± 3 days. The anlotinib cycles and sintilimab cycles will be synchronized as much as possible by adjustments of permissible time windows.

The adverse reactions caused by **anlotinib** can be managed with symptomatic treatment, drug discontinuation, and/or dose modification. It is recommended that the dose be adjusted under the physician's guidance according to the severity of the adverse reaction: ① First dose modification: 10 mg, qd; ② Second dose modification: 8 mg, qd. If a third dose modification is required, the drug should be permanently discontinued.

When on 8 mg doses, the dose can be increased to 10 mg if necessary, depending on the adverse reaction.

When a drug-related adverse reaction occurs, the general rules in Table 3 should be consulted for dose modifications. When adverse reactions such as abnormal liver function [including ALT elevation, AST elevation, or total bilirubin elevation], proteinuria, decreased platelet count, or a bleeding event occur, dose modification and management are performed according to the principles in Tables 4–7.

Table 3. General rules of anlotinib dose modification for various grades of adverse reactions

Adverse reaction grade	Dosing time	Dose modification principle
Grade 3	Drug interruption until adverse reaction resolves to grade <2	Subsequent doses are reduced by one level; If the patient does not recover after 2 weeks, consider permanent discontinuation of the drug.
Grade 4	Drug interruption until adverse reaction resolves to grade <2	Subsequent doses are reduced by one level. Consider permanent drug discontinuation if the patient does not recover after 2 weeks, or consider permanent drug discontinuation based on the physician's judgment.

Table 4. Dose modification principles and management recommendations in case of abnormal hepatic function

Adverse reaction grade	Dose modification principle	Management recommendations

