6.5 Precautions for anlotinib

Bleeding: VEGFR inhibitor antineoplastic agents may increase the risk of bleeding. In clinical studies of anlotinib, this product increased the risk of hemoptysis. However, the clinician should be reminded to pay close attention to this risk.

This product should be used with caution in patients with coagulation abnormalities. Prothrombin time and international normalized ratio should be closely monitored when using this product. The drug should be interrupted if a Grade 2 bleeding event occurs, and drug treatment should be continued at a dose reduced by one level after AE resolves to Grade <2 within 2 weeks. The drug should be permanently discontinued if a Grade 3 or above bleeding event occurs.

Blood pressure increase: A blood pressure increase is the most common adverse reaction of this product. In clinical studies, it was observed that anlotinib could mildly to moderately increase blood pressure. This AE occurs 1 week after dosing and can normally be controlled with conventional antihypertensive medications. **Blood pressure should be monitored every day in the first 6 weeks of dosing.** Blood pressure should be periodically monitored in subsequent doses, and active communication with the physician is required when blood pressure increases. Conventional antihypertensive treatment can mostly control the blood pressure increase. An uncontrollable blood pressure increase can usually be relieved by dose reduction or discontinuation of this product.

If a blood pressure increase occurs, antihypertensive treatment or dose modification of this product should be performed under the guidance of the specialist. Drug interruption is recommended if a Grade 3/4 blood pressure increase occurs. If a Grade 3/4 blood pressure increase recurs after dosing is resumed, subsequent doses can be reduced by one level. Drug discontinuation is recommended if the adverse reaction persists. This product should be discontinued in patients who develop a hypertensive crisis.

Cardiotoxicity: It was observed in clinical studies that anlotinib could cause electrocardiogram abnormalities, including a prolonged QT interval. The drug should be used with caution in patients with a known medical history of a prolonged QT interval (QTc \geq 480

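### The blood pressure monitoring asked for in 6.5 is in neither Table 1 nor 8.2, whose fixed readings from cycle 2 on come after the anlotinib-free week, so hypertension is not ascertained in a standard way

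*Protocol*

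**What the plan says.** **Fixed schedule.** Section 8.2 lists, for the treatment period, "Physical examination: weight, vital signs, ECOG scoring once before each dose". Footnote 2 to Table 1 confirms that blood pressure is covered: "Vital signs include body temperature, pulse, respiratory rate, and blood pressure". The vital-signs row of Table 1 is marked at screening and on Day 1 from cycle 2. The routine-blood row is also marked at the day 8 and day 15 contacts.

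**Dosing.** Section 5.2 gives anlotinib as "12 mg/tablet, qd, po, d1-d14, q3w". Section 6.4 delays later doses where needed so that "the dosing interval between anlotinib treatment cycles is 21 ± 3 days".

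**Precautions.** Section 6.5 states: "A blood pressure increase is the most common adverse reaction of this product". It places the rise 1 week after dosing and continues: "Blood pressure should be monitored every day in the first 6 weeks of dosing". For the time after that it says: "Blood pressure should be periodically monitored in subsequent doses". No interval is given.

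**Other relevant text.** The adverse-event item in 8.2 names blood pressure abnormalities among the things to watch closely while the drugs are given. Table 1 collects adverse events from consent to 30 days after the last dose. The safety visit, 30 ± 3 days after the last dose, records vital signs again.

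**The concern.** Two parts of the protocol describe blood pressure measurement, and only one is a schedule that a site would work from. The scheduled part takes its readings before the Day 1 dose, at the end of the anlotinib-free week. The part that asks for readings while the patient is on the drug sits in a precautions section, with no visit, no CRF field and, after week 6, no frequency.

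The incidence of adverse events is a secondary objective (2.2), and events are graded by CTCAE v4.03. A blood pressure grade depends largely on a measured value, so the hypertension rate depends on when and how often someone measures. Section 6.5 also ties interruption and dose reduction of anlotinib to Grade 3/4 rises, so uneven measurement can affect exposure as well as the safety table.

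**Working it through.** The protocol states no figure to reproduce here. The check is a count of days and readings.

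**Inputs**
- Anlotinib days: 1 to 14 of each cycle (5.2)
- Cycle interval: 21 ± 3 days, that is 18 to 24 (6.4)
- Fixed vital signs: before the dose on Day 1 (8.2, Table 1)
- Daily monitoring: first 6 weeks = 42 days (6.5)
- Day 8 and day 15 contacts: window ± 3 days (Table 1)

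**1. Days off anlotinib before a fixed reading, from cycle 2**

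Gap = interval − 14.
- Nominal: 21 − 14 = 7 days
- Shortest: 18 − 14 = 4 days
- Longest: 24 − 14 = 10 days

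Table 1 also lets Day 1 assessments be made up to 3 days early. If that applies to vital signs, the nominal gap shrinks to 7 − 3 = 4 days, and in the extreme case to 4 − 3 = 1 day. The reading is still off drug. The cycle 1 reading comes before any drug.

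**2. Readings in days 1 to 42**

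| Source | Readings | Within the on-drug stretch |
|---|---|---|
| 6.5, daily | 42 | 2 × 14 = 28 on dosing days |
| 8.2 and Table 1 | 2 (days 1 and 22) | none; both precede that day's tablet |

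Day 1 is itself a dosing day. What matters is that the reading is taken before that cycle's first tablet.

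**3. After day 42**

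The fixed schedule continues with one pre-dose reading on Day 1 of each cycle. Section 6.5 adds an unspecified number. The total cannot be stated, because periodic monitoring has no defined interval. The daily period spans two cycles. For a patient who reaches the 24-month maximum for sintilimab, taken as about 104 weeks, that is 6/104 = 5.8% of the time on treatment.

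**4. Which existing contacts fall on drug**
- Day 8 ± 3 = days 5 to 11: wholly within days 1 to 14.
- Day 15 is nominally one day after the last tablet; with ± 3 it is days 12 to 18, so it may or may not be on drug.
- The maintenance column of Table 1 shows one time point per cycle and no day 8.

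**5. What cannot be computed**

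The protocol gives no hypertension rate, no figure for blood pressure recovery in the off week, and no anlotinib half-life. The effect on the recorded incidence therefore has no defensible number.

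**The case against.** The strongest reply is that the passages do not exclude one another. A site can take vital signs on Day 1 and also follow 6.5. The adverse-event item in 8.2 names blood pressure abnormalities, with no week-6 limit, and adverse events are collected continuously. Since 6.5 puts onset 1 week after dosing, daily readings over two full cycles would cover the usual time of onset. All of this stands. It rules out saying that blood pressure is taken only before Day 1 doses, or that monitoring ends at week 6.

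It does not close the gap. The adverse-event item sets no day or frequency, and continuous collection cannot record a raised value that nobody measured. The safety-visit reading is off drug too. A site working from Table 1 would take no fixed reading during days 2 to 14 of any cycle.

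Two cautions apply to the text itself. The Table 1 marks come from a machine-read table, and its vital-signs row shows no mark at the safety visit although the text of that section requires vital signs there, so blank cells alone are weak evidence. Section 8.2 gives the same pre-dose timing in words. And 8.2 speaks of each dose while anlotinib is taken daily; Table 1, which places the row on Day 1, supports reading this as the Day 1 dose.

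A reader might go further and infer that hypertension is under-measured overall, or that its recorded rate must fall after week 6 by design. The documents support neither. If the 6.5 readings are taken and recorded, the early period is well covered. The later frequency is unknown rather than known to be low. Safety is to be summarised descriptively with percentages, with no planned comparison of early and late periods. Nor would an assumed half-life settle it, because remaining drug exposure is not the same as remaining blood pressure effect.

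**Conclusion.** The point holds as a failure to reconcile 6.5 with the schedule, with a consequence for measurement. From cycle 2 every fixed on-treatment reading falls after the anlotinib-free days, nominally 7 and between 4 and 10 with the interval window. The 42 daily readings implied by 6.5 appear in neither Table 1 nor 8.2, and the frequency after week 6 is undefined. Ascertainment of the drug's most common reaction is thus not standardised, and may be uneven between the first 6 weeks and later.

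This rests on two assumptions: that the anlotinib and sintilimab cycles stay synchronised, which 6.4 seeks as far as possible, and that Day 1 is the intended time for vital signs. The size of any effect on the reported hypertension rate is unknown. The primary endpoint, ORR, and the two-stage design do not depend on these readings. The point merits correction because the remedy costs very little.

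**What to change.** 1. Reconcile Table 1 and 8.2 with 6.5, so that the readings 6.5 asks for are scheduled, the later interval is defined, and the values are captured in the CRF.
2. Where the day 8 contact for blood counts already takes place, record a blood pressure value there. Each such cycle then has one on-drug reading. Day 15 does not serve this purpose, because it is nominally one day after the last tablet.
3. If the schedule is left as it is, report hypertension incidence separately for the first 6 weeks and after. This shows the possible unevenness but does not remove it.

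**Cost.** Item 2 adds one entry per cycle at an existing contact and no new visit, provided the patient is seen in person for the blood count. Item 1 needs a schedule amendment and CRF fields. Item 3 is a reporting change only. No dose or stopping rule is proposed; which monitoring frequency is clinically right is for the investigators to settle.

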8.3 Safety visit

8.4 The safety follow-up is performed 30 ± 3 days after the last dose or before new antineoplastic therapies. The safety visit includes the following activities: Recording of vital signs, weight, physical examination, ECOG-PS score, 12-lead electrocardiography, routine blood/blood chemistry/urine results, coagulation function results, thyroid function, adverse event evaluation, concomitant medications, and subsequent antineoplastic treatment (if applicable).

8.5 Survival visit

An outpatient or telephone follow-up will be performed 1 month after the last dose for every subject; adverse events and concomitant medications within 1 month of the end of treatment will be recorded. Subsequent follow-up on overall evaluation data will be performed until disease progression or new antineoplastic treatment starts. Subsequent antineoplastic treatment and its start date will be recorded, and survival follow-up will be performed.

If the subject withdraws from the study due to toxicity symptoms, withdrawal of informed consent, and disease progression, it will be considered the end of treatment. The reason for treatment discontinuation, the treatment end date, and the withdrawal date will be recorded. At the end of treatment, adverse reactions and concomitant treatments within 30 days after the last dose of the investigational drug will be collected.

9. Efficacy Evaluation

9.1. Tumor imaging and disease evaluation principles

Tumor radiologic examinations usually include contrast-enhanced CT or MRI. The examination sites must include the chest, abdomen, and pelvic cavity. Cranial MRI scans must be performed at baseline for patients with suspected signs or symptoms of central nervous system metastases. Radiologic examinations received by a subject during the study period should be of the same type. Radiologic examinations will be performed on other suspected affected sites (such as the cranium) based on the subject's clinical signs and symptoms. Contrast-enhanced CT is the tumor evaluation method of choice. MRI will be used if contrast-enhanced CT is contraindicated. Slices of 10 mm or thinner are used for chest, abdominal, and pelvic CT and MRI scans, and 5 mm slices for continuous spiral CT scans. For clinically measurable superficial lesions (such as skin nodules, palpable lymph nodes), a color photograph containing a scale to show the lesion dimensions used to estimate lesion size is recommended.

During the screening, the study site investigator will confirm the presence of measurable lesions based on RECIST1.1 and irRECIST criteria to confirm the subject's eligibility. There should be a maximum of 5 target lesions in total and 2 target lesions per organ.

During the screening, the first tumor radiologic examination must be performed within 28 days before treatment. Evaluation is performed once after the 2nd treatment cycle (C3) and once after the 4th treatment cycle (C5). Subsequently, an evaluation will be performed once after the 7th cycle (C8) and once after the 10th cycle (C11). After the 10th cycle, an evaluation will be performed once every 4 treatment cycles, and the time window for radiologic evaluation is ± 7 days. Additional examinations can be performed if clinical progression occurs. The investigator will simultaneously evaluate RECIST1.1 and record the results, but this will not be used as a reference for treatment. After the investigator has completed the first radiologic evaluation of disease progression based on irRECIST, current treatment can be continued if the patient has stable clinical disease; radiologic evaluation will be performed after 4–6 weeks for confirmation (based on irRECIST). Treatment will be discontinued if progression is confirmed. If progression is not confirmed, study treatment can be continued until PD is confirmed by radiologic evaluation. An unscheduled radiologic evaluation can be performed at any time if the patient suffers unstable clinical disease during the study.

The definition of unstable clinical disease is as follows:

- Development of clinically significant signs and symptoms suggesting disease progression (including worsening laboratory test values)
- Decrease in ECOG PS score

- Rapid disease progression
- Tumor progression at important anatomical sites that requires other emergency medical interventions (such as spinal cord compression)

Patients who require treatment discontinuation for reasons other than disease progression shown in the radiologic evaluation should undergo radiologic evaluation at the end of treatment and after that at scheduled time points stipulated in the protocol until any one of the following events occurs: start of new antineoplastic therapy, objective disease progression, withdrawal of informed consent by the subject, loss to follow-up, or death.

Baseline cranial CT/MRI examination should be performed before starting study treatment in subjects with known or suspected brain metastases at screening. During the study period, cranial CT/MRI evaluation should be performed on these subjects, and brain metastases are considered non-target lesions for evaluation.

If the investigator cannot determine whether disease progression has occurred, particularly for non-target lesions and new lesions, the subject can continue treatment until clinical symptoms occur or the next scheduled evaluation where radiologic evaluation is repeated. If disease progression is confirmed, then the date of progression should be the initial date of discovery. For subjects who discontinue treatment due to treatment completion or reasons other than objective disease progression, radiologic tumor evaluation should be performed once at treatment completion/discontinuation. A subsequent radiologic evaluation should be performed according to a protocol-stipulated radiologic examination schedule until one of the following situations occurs: start of new antineoplastic therapy, objective disease progression, death, or end of the study, whichever comes first.

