	
significant clinically rapid progression or patients with an unstable general condition.
 
 3. The cumulative treatment period with anti-PD-1 antibody reaches 2 years; 4. Radiological examination shows that drug discontinuation can be considered for CR subjects who have completed 6 cycles of drug administration. 5. Intolerable toxicity; 6. Poor compliance; 7. Loss to follow-up. 8. The investigator considers that the subject must withdraw from the study.
Treatment regimen	
IBI308: Product name (sintilimab), 200 mg intravenous infusion, qd, d1, q3w,
 
Anlotinib: 12 mg/tablet, one tablet daily, orally half an hour before breakfast, d1–d14, and 1 treatment cycle lasting 3 weeks. The patient will take the study drug until protocol-stipulated treatment withdrawal criteria are fulfilled.

Sample size calculation Statistical methods	
Simon's 2-stage design was used for sample size estimation. An alpha of 0.05 (one-tailed), a beta of 0.2, and a power of 0.8 were used. Based on existing literature, the objective response rate (ORR) of anti-PD-1 monoclonal antibody monotherapy in advanced or PD-L1-positive recurrent endometrial carcinoma after failure of first-line chemotherapy is 13%.
 
Assuming that IBI308 combined with anlotinib can increase efficacy by 26%, the ORR is 39%. At least 23 patients are needed. Seven patients will be enrolled in stage 1. When the number of valid patients < 2, combination therapy is considered not superior to monotherapy, and this trial will be terminated. Otherwise, 16 subjects will be enrolled in stage 2. The trial is rejected if there are ≤5 patients with ORR in the two stages. Percentages, χ^2 test, and analysis of variance are used to analyze efficacy. Descriptive methods and percentages will be used for safety analysis.

Efficacy evaluation	
RECIST (v1.1) and irRECIST criteria are used for radiologic tumor evaluation after the 2nd treatment cycle (\pm 7 days) and after week 4 (\pm 7 days) after the start of dosing. Subsequently, radiologic tumor evaluation will be performed once every 3 treatment cycles (\pm 7 days) until the 10th cycle. After the 10th cycle, radiologic tumor evaluation will be performed every 4

	treatment cycles (\pm 7 days). Additional examinations can be performed if clinical progression occurs.

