14. Tumor evaluation includes irRECIST and RECIST 1.1. Radiologic tumor examinations usually include contrast-enhanced CT or MRI. The examination sites must include the chest, abdomen, and pelvic cavity. Enhanced cranial MRI scan must be performed at baseline for patients with suspected signs or symptoms of central nervous system metastases. The type of radiologic examinations received by a subject during the study period should be the same. Baseline evaluation will be performed within 28 days before the first dose. Radiologic tumor evaluation will be performed once in Week 2 (± 7 days) and Week 4 (± 7 days) after the start of dosing. Subsequently, radiologic tumor evaluation will be performed once every 3 treatment cycles (± 7 days) until the 10th cycle. After the 10th cycle, radiologic tumor evaluation will be performed once every 4 treatment cycles (± 7 days). After the investigator has evaluated the first radiologic progression based on irRECIST, current treatment can be continued if the patient has stable clinical disease without significant progression, and radiologic evaluation will be performed after 4–6 weeks for confirmation (based on irRECIST). If progression is not confirmed, study treatment can be continued.

1. Study Background and Theoretical Basis

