4.4. Withdrawal criteria

If any of the following situations occur during this trial, the investigator must discontinue the trial and withdraw the subject. Before withdrawal, the investigator must complete the last evaluation of various markers. The reason and date of the subject's withdrawal will be recorded in detail, and a safety visit shall be performed within 30 days after withdrawal.

- (1) The subject withdraws informed consent and requests to withdraw from the trial;
- (2) Radiological examinations show tumor progression;

*If the subject's clinical disease is stable without significant progression, existing treatment can be continued after a discussion is held with the patient, and informed consent is obtained. Following this, a radiologic evaluation will be performed after 4–6 weeks for confirmation, and treatment can be discontinued if progression is reconfirmed.

- (3) Occurrence of serious adverse events;
- (4) Occurrence of intolerable toxicity;
- (5) Other complications that in the investigator's judgment, make it inappropriate for the subject to continue;
- (6) The subject has poor compliance and does not take the drug on time or at the prescribed dose or does not comply with the study procedures;
- (7) Simultaneous use of other antineoplastic drugs;
- (8) Death of the Subject;
- (9) Loss to follow-up.

5. Investigational Drug and Treatment Design

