Appendix 1. ECOG Scale of Performance Status (ECOG PS).

Activity score	Description
0	Asymptomatic, fully active, able to carry on all pre-disease activities without restriction.
1	Symptomatic, restricted in physically strenuous activity but ambulatory, and able to carry out work of a light or sedentary nature, such as light housework and office work.
2	Symptomatic, ambulatory, and capable of self-care but unable to carry out any work activities, up and about >50% of waking hours.
3	Symptomatic, capable of only limited self-care, confined to bed or chair more than 50% of waking hours, but is not bedridden.
4	Completely disabled, cannot carry on any self-care, bedridden.
5	Dead.

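### The ECOG criterion for unstable clinical disease in section 9.1 runs the wrong way on the protocol's own scale

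*Protocol*

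**What the plan says.** Section 9.1 lists four criteria for unstable clinical disease. Three describe deterioration: clinically significant signs or symptoms that suggest progression, rapid progression, and progression at an important anatomical site that needs urgent intervention. The remaining one, second in the list, is "Decrease in ECOG PS score".

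Appendix 1 gives the scale. Score 0 is "Asymptomatic, fully active, able to carry on all pre-disease activities without restriction", score 4 is "Completely disabled, cannot carry on any self-care, bedridden", and score 5 is death. Section 4.1 admits patients with scores of 0 to 2, which uses the scale in the same direction.

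Clinical stability is then used in two kinds of decision:

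- **Unscheduled imaging.** Section 9.1: "An unscheduled radiologic evaluation can be performed at any time if the patient suffers unstable clinical disease during the study".
- **Treatment after a first irRECIST progression.** Table 1, footnote 14: "current treatment can be continued if the patient has stable clinical disease without significant progression". Section 9.1 has a similar rule, and section 4.4 allows continuation where the "clinical disease is stable without significant progression, existing treatment can be continued after a discussion is held with the patient". A confirmatory scan follows after 4 to 6 weeks.

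**The concern.** A list meant to identify patients who are getting worse contains one item that, as worded, identifies patients who are getting better. It is also the only one of the four that rests on a numerical score, and section 8.2 has that score recorded before every dose. That makes it the easiest item for site staff or a monitor to apply mechanically.

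What is at stake is operational and concerns patient safety. Under section 9.1, RECIST 1.1 readings do not guide treatment. In the weeks between a first irRECIST progression and its confirmation, clinical stability is therefore a main consideration in deciding whether dosing goes on. A patient whose only sign of decline is a rising ECOG score would not meet the literal definition of instability, while a patient whose score improves would.

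**Working it through.** The protocol gives no figure to reproduce here. The check compares the direction of the criterion with the direction of the scale, then counts what the criterion can flag.

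**Direction.** In Appendix 1 each higher score describes a worse state, from no symptoms (0) to death (5). A decrease in score is therefore an improvement. No other section corrects the criterion or defines ECOG change the other way.

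**Inputs for the count.** Entry score b is 0, 1 or 2 (section 4.1). On-study score a in a living patient is 0 to 4 (Appendix 1). A worsening is a > b; an improvement is a < b.

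| Entry score | Possible worsenings (4 − b) | Possible improvements (b) |
|---|---|---|
| 0 | 4 | 0 |
| 1 | 3 | 1 |
| 2 | 2 | 2 |
| Total | 4 + 3 + 2 = 9 | 0 + 1 + 2 = 3 |

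- As written, the item flags 0 of 9 worsenings and 3 of 3 improvements.
- With the direction corrected, it flags 9 of 9 worsenings and 0 of 3 improvements.
- The largest worsening in a living patient is 4 − 0 = 4 steps, and the item as written does not register it.
- A patient who enters at ECOG 0 can never meet the item relative to baseline, because the score cannot fall below 0.

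**Reference point.** The protocol does not say whether change is measured from entry or from the previous visit. Measured between visits, with both scores from 0 to 4, there are 4 + 3 + 2 + 1 + 0 = 10 worsenings and 10 improvements. The item as written flags 0 of 10 and 10 of 10, so the conclusion is the same.

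**The case against.** The best case on the other side is that this is a wording slip with little practical effect.

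- **The meaning is evident.** The list is headed as unstable disease and its other three items all describe worsening. An oncology investigator is unlikely to treat a move from ECOG 2 to 1 as instability. This is a fair point and lowers the weight, but the operative text still states the opposite of what is meant.
- **Other criteria overlap.** The first criterion covers clinically significant signs and symptoms, and Appendix 1 grades ECOG partly by symptoms: a patient who rises from 0 has become symptomatic. Most deteriorating patients would be caught. What remains is a rise in score that the investigator does not otherwise read as a sign of progression.
- **Other routes exist.** Continuing treatment is permitted, not required. The synopsis exempts from confirmation cases of "significant clinically rapid progression or patients with an unstable general condition". Section 4.4 also provides for withdrawal for serious adverse events, intolerable toxicity or complications that the investigator judges to rule out continuing. Section 9.1 and the synopsis separately allow extra examinations on clinical progression. Nothing obliges a deteriorating patient to stay on treatment because of this criterion.
- **The link to other sections is loose.** Footnote 14 and section 4.4 speak of stable disease without referring to the section 9.1 definition. That is correct, so the definition informs those decisions but does not formally control them.
- **The counts do not measure impact.** They follow from the word used and describe score changes on one item. They say nothing about how many patients would be affected.

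All of this limits the severity. None of it makes the criterion correct.

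**Conclusion.** The criterion is reversed on the protocol's own scale. It is a minor point and the finding itself is certain. As written, the item flags none of the 9 possible worsenings from entry and all 3 possible improvements. The documents give no frequency for patients whose only sign of decline is the ECOG score; the assumption here is that it is low.

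The effect on the trial's results is small. Sample size, alpha, power, the Simon boundaries and RECIST 1.1 readings do not depend on this item. Timing of confirmed progression is protected by the rule in section 9.1: "If disease progression is confirmed, then the date of progression should be the initial date of discovery". Any effect on irRECIST endpoints would be confined to rare cases of unconfirmed progression or pseudoprogression.

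**What to change.** In section 9.1, replace the criterion with *increase in ECOG PS score (worsening performance status)*. It would help to state the reference point, entry or previous visit, in the same line. A short cross-reference from Table 1 footnote 14 and section 4.4 to this definition would make clinical stability mean the same thing throughout, but the correction does not depend on it.

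The cost is a few words in an amendment. No visits, assessments or data are added, because section 8.2 already has ECOG scored before each dose.
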